6. TRIAL PARTICIPANT DISPOSITION

6.1 Disposition of Participants

Participant disposition will be summarized using a CONSORT flow diagram. This will display the number of participants screened for eligibility, the number excluded (with reasons), the number who underwent CMV IgG testing, the number randomized to each treatment arm, and the number who received or did not receive the assigned intervention (with reasons for non-receipt). The diagram will also present the number of participants who discontinued follow-up—such as due to adverse events, loss to follow-up, or protocol noncompliance—and the number included in the primary analysis. A summary table may also be provided to supplement the flow diagram with arm-specific details.

6.2 Treatment Exposure

Treatment exposure will be summarized in a table using data from the Daily Study Product Administration Form. The number of study product doses administered will be summarized using descriptive statistics, including the mean, standard deviation, median, and interquartile range (IQR), stratified by study site. The number of renal dose adjustments will also be summarized and categorized by site.

6.3 Protocol Deviations

All protocol deviations will be reviewed by the study team to ensure appropriate categorization. Assessment, remediation, and prevention measures will be documented and updated as needed. A summary table will present the number and types of protocol deviations by site, accompanied by a detailed listing of each deviation.

Listing: Protocol Deviations and Enrollment Violations by Site

Subject ID	Site	Type of Deviation	Deviation Date	Assessment	Remediation/prevention
Subject 1	Site 1				
Subject 2	Site 2				
...

7. BASELINE DATA

Unless otherwise specified, baseline characteristics will be summarized descriptively using appropriate summary statistics. Continuous variables will be summarized using the mean and standard deviation, median, interquartile range, and range. Categorical variables will be summarized using frequencies and percentages. All summaries will be presented overall and stratified by treatment group.

Screening

The number of participants screened and enrolled, along with the reasons for non-enrollment (e.g., ineligibility), will be summarized by site for all participants screened for the GRAIL 3 study.

Demographic

Baseline demographic characteristics, obtained from the Demographics Case Report Form (CRF), will be summarized by treatment group.

Respiratory Support

Baseline respiratory support data, as recorded in the Demographics CRF, will be summarized by treatment group.

Laboratory Results

Baseline laboratory values will be summarized by treatment group using data from the Participant Daily Status CRF, APACHE III – Acute Physiology CRF, and Safety Labs CRF.

CMV testing

CMV testing results from ELISA and LFA assays for all **screened** participants will be summarized using contingency tables.

8. PRIMARY ENDPOINT ANALYSES

The primary endpoint, respiratory-support-free days (RSFDs), is defined as 28 days minus the number of days a participant received respiratory support (including invasive mechanical ventilation, non-invasive ventilation with CPAP or bi-level CPAP and PEEP ≥ 5 cmH₂O, or high-flow nasal cannula oxygen with a flow rate ≥ 30 L/min) through Day 28 following randomization.

- Participants who do not survive through Day 28 will be assigned zero RSFDs.
- Participants who remain on respiratory support on Day 27 will be assigned zero RSFDs.
- Participants transferred to long-term acute care hospitals (LTACHs) will be assigned zero RSFDs.
- Participants who withdrew consent, refused further participation by themselves or a legally authorized representative (LAR), and for whom no further data were collected, or who withdrew due to study closure within the first 28 days will be considered missing for the RSFD endpoint.

RSFDs will be summarized descriptively using the mean, standard deviation, median, and range by treatment group. To formally test the primary hypothesis that the mean difference in RSFDs between treatment arms differs from zero, a two-sample parametric t-test will be used. This test is appropriate even if the normality assumption is mildly violated, given its robustness for moderate sample sizes ($n > 25$). As a confirmatory approach, a two-sample permutation t-test will also be performed. This nonparametric test does not require distributional assumptions and is valid under the weaker condition of exchangeability, which is satisfied in the randomized trial setting.

To further improve statistical efficiency and precision, the semiparametric efficient and robust method of Davidian et al. [7, 8] will be employed to estimate the mean difference between arms, along with its 95% confidence interval. This method adjusts for baseline characteristics predictive of the primary outcome and is more powerful than a conventional ANCOVA or t-test when baseline adjustment is warranted. If data on

the primary endpoint are missing for reasons other than death, the analysis will appropriately account for the missing data mechanism, as described in Protocol Section 6.4.1.

In addition to the ITT analysis, the primary endpoint will also be analyzed in a classical intent-to-treat (cITT) and two modified intent-to-treat (mITT) populations.

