2.2 Study Objectives and Endpoints

Primary Objective: To evaluate whether administration of ganciclovir increases respiratory-support-free days (RSFDs) in immunocompetent patients with sepsis-associated acute respiratory failure.

Primary Endpoint: RSFDs will use a “last off” approach (detailed in Protocol V5 Section 6.1.1), meaning that RSFDs will be counted when a participant gets off and stays off of respiratory support (as defined in Protocol V5 Section 4.1.1) to day 28. Participants who do not survive through day 28 are assigned zero RSFDs.

Secondary Objectives:

1. To evaluate whether administration of ganciclovir increases VFDs in immunocompetent patients with sepsis-associated acute respiratory failure.
2. To evaluate whether administration of ganciclovir increases total RSFDs (all RSFDs, instead of last-off approach) in immunocompetent patients with sepsis-associated acute respiratory failure.
3. To evaluate whether mortality and time to death in the 28 and 180 days is different among ganciclovir recipients relative to placebo recipients, respectively.
4. To evaluate whether duration of mechanical ventilation among survivors in the first 28 days is different among ganciclovir recipients relative to placebo recipients.
5. To evaluate whether duration of respiratory support among survivors in the first 28 days is different among ganciclovir recipients relative to placebo recipients.
6. To evaluate whether oxygenation is different among ganciclovir recipients relative to placebo recipients.
7. To evaluate whether ICU-free days in the first 28 days are different among ganciclovir recipients relative to placebo recipients.
8. To evaluate whether CMV DNA detection in plasma and endotracheal aspirate (ETA) by day 28 is different among ganciclovir recipients relative to placebo recipients.
9. To assess the number and severity of reportable adverse events and reportable serious adverse events in the first 28 days in both groups.

Secondary Outcomes:

1. VFDs (defined to be 28 days minus the duration of mechanical ventilation through day 28 since randomization [a key secondary endpoint]). Participants who do not survive through day 28 are assigned zero VFDs.
2. Total RSFDs (calculated as 28 days minus each day of respiratory support through day 28 since randomization). Participants who do not survive through day 28 are assigned zero respiratory-support-free ventilator-free days.
3. Mortality by day 180 (day 28, day 180, time-to-event).

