5. GENERAL ANALYSIS METHODS

Primary Endpoint

To evaluate the primary hypothesis—that the mean difference in respiratory support-free days (RSFDs) between the two treatment groups is significantly different from zero—we will use a two-sample parametric t-test as the primary statistical test. This test is known for its robustness to violations of normality when the sample size is sufficiently large ($n > 25$), as is the case in this trial.

To support and validate the primary analysis, we will also conduct a two-sample permutation t-test. This nonparametric test requires only the assumption of exchangeability, which is satisfied in the context of a randomized controlled trial. The permutation test provides a distribution-free confirmatory approach, reinforcing the robustness of our findings.

In addition, we will apply the semiparametric efficient and robust estimation procedure proposed by Davidian et al. [7,8] to estimate the mean treatment difference in RSFDs along with a 95% confidence interval. This method adjusts for baseline covariates predictive of the outcome, thereby improving both statistical efficiency and precision relative to unadjusted comparisons or traditional ANCOVA. This analysis also accommodates missingness in the primary endpoint (excluding death) by explicitly modeling the missing data mechanism, as described in Protocol Section 6.4.1.

In addition to the primary analysis using the main intent-to-treat (ITT) population, we will conduct sensitivity analyses using the classical ITT (cITT) and two modified ITT (mITT) analysis sets to assess the robustness of results.

Secondary endpoints

For quantitative secondary endpoints, including the key secondary endpoint of ventilator-free days (VFDs), we will apply the same analytic approach as described for the primary endpoint (RSFDs), including both unadjusted and adjusted methods using the semiparametric efficient and robust procedure proposed by Davidian et al. [7, 8]. In addition, analyses will be conducted on total RSFDs without the last-off approach, to assess consistency across definitions.

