10. SECONDARY ENDPOINTS ANALYSES

Each secondary endpoint will be analyzed and summarized using appropriate statistical methods, and results will be presented by treatment group unless otherwise specified. Tables or figures will be used where appropriate.

1. Ventilator-Free Days (VFDs) defined as 28 days minus the total duration (in days) of invasive mechanical ventilation during the first 28 days post-randomization.
 - Participants who do not survive through Day 28 will be assigned 0 VFDs.
 - Participants who remain mechanically ventilated on Day 27 will be assigned 0 VFDs.
 - Participants transferred to long-term acute care hospitals (LTACHs) will be assigned 0 VFDs.
 - Participants who withdraw from the study will be considered as having missing data.Differences in VFDs between treatment arms will be analyzed using a two-sample parametric t-test. Descriptive statistics (mean, standard deviation, median, quartiles, and range) will also be presented in summary tables.
2. Total RSFDs without last-off approach defined as 28 minus the cumulative number of days on any form of respiratory support within 28 days of randomization, without the last-off rule applied. Participants who die before Day 28 will be assigned 0 RSFDs.

Differences in RSFDs between treatment arms will be analyzed using a two-sample parametric t-test. Descriptive statistics (mean, standard deviation, median, quartiles, and range) will also be presented in summary tables.

3. Mortality will be evaluated as a time-to-event outcome through 28 days and 180 (± 42 days). Analyses will mirror those described in Section 9, including Kaplan–Meier survival curves, log-rank tests, and Cox proportional hazards models (adjusted and stratified by baseline creatinine clearance). In addition, we will test for an interaction between treatment group and period (during- vs. post-treatment) to determine if treatment effects on mortality vary over time.
4. Duration of mechanical ventilation among participants who survive through Day 28, the total number of days on invasive mechanical ventilation will be calculated. Participants transferred to LTACHs will be assigned 28 days. Differences between treatment arms will be analyzed using a two-sample parametric t-test. Descriptive statistics (mean, standard deviation, median, quartiles, and range) will also be presented in summary tables.

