5. Duration of respiratory support (with Last-Off Approach) among Day 28 survivors, the number of days on any qualifying respiratory support (applying the last-off approach) will be summarized. Participants transferred to LTACHs will be assigned 28 days. Differences between treatment arms will be analyzed using a two-sample parametric t-test. Descriptive statistics (mean, standard deviation, median, quartiles, and range) will also be presented in summary tables.
6. Oxygenation ($\text{PaO}_2/\text{FiO}_2$ ratio) measured daily on study days 1–7 will be visualized using boxplots stratified by treatment arm.
7. ICU-free days, defined as 28 minus the number of days in the intensive care unit (ICU) during the first 28 days post-randomization.
 - Participants who do not survive through day 28 will be assigned zero ICU-free days.
 - Participants who remain in the ICU on day 27 will be assigned zero ICU-free days.
 - Participants who are transferred to LTACH facilities will be assigned zero ICU-free days.
 - Participants who withdraw from the study will be considered as having missing data.Differences in ICU-free days between treatment arms will be analyzed using a two-sample parametric t-test. Descriptive statistics (mean, standard deviation, median, quartiles, and range) will also be presented in summary tables.
8. CMV DNA detection in plasma and endotracheal aspirate (ETA) by day 28 (>0 IU/mL, >1000 IU/mL), defined as positive CMV PCR from ETA, plasma, or serum specimens.
The analysis will be conducted by the unblinded protocol statistician.
Differences in CMV DNA detection in plasma and endotracheal aspirate between treatment arms will be evaluated under the competing risk framework of Fine and Gray (10). Cumulative incidence estimates will be evaluated, and Gray's test p-value will be used to test the difference between arms accounting for death as competing risk.
 - This analysis will include death as a competing risk if it occurs on the same day of the last negative CMV test date.
 - Any CMV reactivation will be considered, even those which were below the level of quantification but greater than 0.
9. A comprehensive list of all reportable AEs of Grade 3 or higher by day 28 will be provided, including onset date, AE verbatim, MedDRA code, SAE/EAE, study day, severity grade, relationship to study drug, outcome, and duration days.

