6 STATISTICAL CONSIDERATIONS

6.1 Power Calculations for Primary and Secondary Hypotheses

6.1.1 Primary Endpoint

The primary endpoint RSFD is defined as follows.

Consistent with use of free-days in other studies, RSFDs will use a “last off” approach. This is the approach that has been used in PETAL Network studies (e.g., NCT02509078), is preferred by FDA as a more durable/sustained recovery landmark, and recommended by our External Advisory Board.

“Last off” means that RSFDs will be counted when a participant gets off and stays off of respiratory support (as defined in Section 4.1.1) to day 28. Days off of respiratory support will be counted back from day 28 to the last day when respiratory support was received. If a participant is still receiving respiratory support on day 28, no RSFDs will be counted, even if they were not receiving support for some number of days before day 28. Following are 3 examples of this calculation:

1. Participant receives respiratory support from days 1-10 and then receives no further respiratory support through day 28. RSFDs=18.
2. Participant receives respiratory support from days 1-10, then again from 16-20, then again from 24-26. No respiratory support is received on days 27 or 28. RSFDs=2.
3. Participant receives respiratory support from days 1-10, then again from 26-28. RSFDs=0.

Participants who do not survive to day 28 are assigned zero respiratory-support-free days [23, 88]. The 28-day landmark is chosen, because

1. Interventional trials in acute respiratory failure typically involve a 28-day treatment or follow-up period after the patient enrolls in the trial; and
2. Most patients with acute respiratory failure have either died or been successfully weaned from respiratory support by day 28 [23, 88].

To estimate the required sample size for the trial with adequate statistical power for the primary endpoint, we used the data of VFDs in the ganciclovir and placebo arms of the GRAIL Phase 2 trial and available RSFD data in the literature [83-85]. The summary statistics of VFDs in the sepsis cohort of GRAIL Phase 2 trial are shown in the table below. Since standard deviation data for RSFD is sparse, we assume that standard deviation for RSFDs is similar to that of VFDs in our sample size calculations as informed by Table 6-1.

Table 6-1. Summary statistics of VFDs in the Sepsis Cohort of GRAIL Phase 2 Trial

	n	Min	Q1	Med	Mean	Q3	Max	StD
Control	66	0	9.0	20	16.33	24	27	9.62
Treatment	71	0	16.5	23	19.07	25	27	9.25

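### SAP 8 defines the primary endpoint without the last-off rule, against SAP 2.2 and protocol 6.1.1, and adds Day-27 and LTACH zero rules that SAP 12 does not list

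*SAP*

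**What the plan says.** The primary endpoint is defined in two ways.

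- **Last-off.** SAP 2.2 says "RSFDs will be counted when a participant gets off and stays off of respiratory support" and refers to protocol 6.1.1. There, "Days off of respiratory support will be counted back from day 28 to the last day when respiratory support was received", and "If a participant is still receiving respiratory support on day 28, no RSFDs will be counted". Three worked examples follow. Death by day 28 scores zero.
- **Plain count.** SAP 8, the section that governs the primary analysis, says "The primary endpoint, respiratory-support-free days (RSFDs), is defined as 28 days minus the number of days a participant received respiratory support". It does not mention last-off or cite protocol 6.1.1 for the definition. It assigns zero for death by Day 28, for support on Day 27 and for any LTACH transfer.

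Other SAP sections keep the two counts apart. Under secondary endpoints, SAP 5 says "analyses will be conducted on total RSFDs without the last-off approach, to assess consistency across definitions". SAP 10 item 2 reads "Total RSFDs without last-off approach defined as 28 minus the cumulative number of days on any form of respiratory support", and its only stated zero rule is "Participants who die before Day 28 will be assigned 0 RSFDs". SAP 10 item 5 is headed "Duration of respiratory support (with Last-Off Approach) among Day 28 survivors".

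The LTACH rule (zero free days, or 28 days of duration) is stated for the primary endpoint, ventilator-free days, ICU-free days and both duration endpoints, but not for total RSFDs. SAP 12, which covers changes from the protocol, mentions only the additional analyses of SAP 11.

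**The concern.** A programmer who follows SAP 8 literally computes a different primary variable from the one in the protocol. Patients who come off support and later return to it are credited with the interim free days that last-off is meant to withhold.

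The comparison in SAP 5 between the primary and total RSFDs also loses its purpose. The two would differ only through the Day-27 and LTACH rules, not through last-off.

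The LTACH rule is a separate matter. It can take a survivor from a high score to zero, so it changes the primary endpoint, yet it is not declared as a change. According to SAP 4, enrollment was closed over safety and futility concerns after a DSMB review, and the DSMB was unblinded (SAP 2.4). Two incompatible primary definitions in one SAP leave a choice open at analysis that should not be open.

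**Working it through.** **Inputs.** Last-off rule and three worked examples: protocol 6.1.1. Primary formula and zero rules: SAP 8. Total RSFDs and last-off duration: SAP 10 items 2 and 5. Planning difference of 2.74 days and SD of 9.4 days: SAP 2.5.

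**Formulas for a patient alive at day 28.**
- Protocol: 28 − last day on support.
- SAP 8: 28 − number of days on support, set to 0 if on support on Day 27 or sent to an LTACH.
- Total RSFDs: 28 − number of days on support.
- Last-off duration, read as the last day on support; 28 if sent to an LTACH.

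**Protocol figures first.** Example 1: 28 − 10 = 18. Example 2: 28 − 26 = 2. Example 3: 28 − 28 = 0. All three match the protocol.

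**SAP 8 on example 2.** Support days are 10 + 5 + 3 = 18, so the score is 28 − 18 = 10.

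| Support days | Protocol | SAP 8 | Total RSFDs | Last-off duration |
|---|---|---|---|---|
| 1–10 (example 1) | 18 | 18 | 18 | 10 |
| 1–10, 16–20, 24–26 (example 2) | 2 | 10 | 10 | 26 |
| 1–10, 26–28 (example 3) | 0 | 0 | 15 | 28 |
| 1–10, 20–21 | 7 | 16 | 16 | 21 |
| 1–10, 28 | 0 | 17 | 17 | 28 |
| 1–27 | 1 | 0 | 1 | 27 |
| 1–10, then LTACH, no further support | 18 | 0 | 18 | 28 |

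The table takes Day 27 as study day 27. The total of 18 in the last row reads the silence of SAP 10 item 2 as no LTACH rule.

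**Internal check.** In a survivor not sent to an LTACH, last-off RSFDs and last-off duration must sum to 28. With SAP 8 the sum is 10 + 26 = 36 in example 2, and 17 + 28 = 45 for support on days 1–10 and 28.

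**How far SAP 8 coincides with total RSFDs.** Take every survivor pattern with support from day 1, one gap and one later episode, without LTACH transfer. There are C(28,3) = 3,276. Support on Day 27 occurs in 2 × C(26,2) = 2 × 325 = 650. SAP 8 equals total RSFDs in the other 3,276 − 650 = 2,626. These are counts of possible patterns, not patient frequencies.

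**Effect on the arm difference.** Shift = difference between arms in the proportion affected × days per affected patient. The documents give no such proportions, so the imbalance is an assumption.
- 1 percentage point: 0.01 × 8 = 0.08 day (return to support, as in example 2) or 0.01 × 18 = 0.18 day (LTACH case).
- 5 points: 0.05 × 8 = 0.4 day or 0.05 × 18 = 0.9 day.
- To equal 2.74 days: 2.74 / 8 = 34 points or 2.74 / 18 = 15 points.
- Equal proportions and equal days per affected patient in both arms: no shift.

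The planned 213 per arm is unaffected, because it rests on the assumed 2.74 and 9.4 days.

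**The case against.** The strongest reply is that last-off is plainly intended. SAP 2.2 states it and points to the protocol's worked examples, SAP 5 and SAP 10 item 2 set the plain count apart, and SAP 10 item 5 applies last-off to duration. Even the Day-27 zero suits a last-off endpoint better than a plain count. This shows that the cause is probably a drafting slip. It does not make SAP 8 correct: SAP 10 says with or without last-off where it matters, SAP 8 says neither, and the Day-27 rule leaves example 2 at 10.

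Day 27 may simply be study day 28 under another numbering. Protocol 9.6 makes the day of randomization study day 1, so study day 28 falls 27 days later. This is possible. On that reading the discrepancies for days 1–27 and for days 1–10 plus 28 disappear, but example 2 does not change. SAP 8 does not say so, and its other rules use Day 28. Under last-off the Day-27 rule costs at most one day.

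The LTACH zero may fill a real gap. Protocol 9.9, 9.11 and 12.2 provide for chart abstraction while the patient is hospitalized and a day-28 call that does not cover respiratory support. Setting such a rule is a proper task for a SAP, but it still has to be declared. SAP 10 item 2 also omits the rule for withdrawals, so its silence on LTACH may be abbreviation. The SAP should say which.

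Finally, no trial-level effect is shown, and matching 2.74 days would take a large imbalance. Both points stand. The need for correction rests on the contradictory definition, not on a demonstrated shift.

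**Conclusion.** The concern holds, and SAP 8 must be corrected. It contradicts SAP 2.2 and protocol 6.1.1 on how the primary endpoint is scored. Example 2 gives 10 instead of 2 under either reading of Day 27. The Day-27 and LTACH zeros are absent from the protocol definition and from SAP 12. The LTACH rule can remove up to 18 days in the case shown, while the Day-27 rule is minor once last-off is restored.

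The patient-level figures are exact, given the stated reading of Day 27. The effect on the treatment difference is unknown. The 0.4 and 0.9 day figures rest on an assumed 5-point imbalance and on constructed patients, and the effect is nil if the arms are balanced in both rates and days.

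**What to change.** 1. In SAP 8, define RSFD as 28 minus the last study day on respiratory support (as defined in protocol 4.1.1), with 0 if dead by day 28 or on support on day 28.
2. Delete the Day-27 rule, or show that it equals day 28 under the study-day numbering. Reconcile the same line for ventilator-free days and ICU-free days in SAP 10.
3. List the LTACH zero in SAP 12 as a change from the protocol, and say whether it applies to total RSFDs.
4. Add one sensitivity analysis that scores LTACH patients by last-off from observed support where status through day 28 is known. Where it is unknown, score 0 if on support at transfer. If off support at transfer, report both bounds: 0, and 28 minus the last observed support day.

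The cost is one corrected definition, one day-numbering reconciliation, one SAP 12 entry and one sensitivity analysis. Support data after LTACH transfer may not exist, which is why bounds are used. No new data collection and no change in sample size are needed.
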